7.2.4. Dose Adjustments, Interruptions, and Delays

No dose reductions (of any study drug) are permitted during this study.

Dosing interruptions of study drugs are permitted for reasons not related to study treatment (for example, minor surgery, unrelated medical events, patient vacation, and/or holidays). The reason for interruption should be documented on the case report form (eCRF).

In addition, doses of study drug(s) may need to be delayed to manage specific AEs or other toxicities. Refer to Section [7.2.4.1](#) for implementation of dose delays due to AEs.

All dose modifications should be documented, including the approach taken and a clear rationale for the need for modification.

7.2.4.1. Dose Delays for Adverse Events

Study treatment may be held for a maximum of 28 days; see exception for an immune-related AE below. If appropriate, and in the opinion of the investigator and upon agreement with the sponsor, study treatment may resume upon resolution of clinically significant AEs to baseline or improvement to Grade <2. If AEs, see exception for an immune-related AE, do not resolve to baseline or improve to Grade <2 within 28 days following the last administered dose, study treatment should be permanently discontinued and the patient should be discontinued from the trial. If treatment is held, the day of treatment should continue as if no drug interruption has occurred. For example, if study drug is held on D6 of a cycle and AEs have resolved by D10 (4 days later), the study drugs should be resumed per the original schedule. If the original schedule results in a study drug being held for >28 days, the study drug may not be resumed. One or both study drugs may be held, resumed, or discontinued.

If the AE is an immune related AE as outlined in [Attachment 7](#), and if the treatment management guidelines outlined in [Attachment 7](#) are followed and documented in the patient's medical record, treatment may be held for >28 days to allow taper of high dose steroids. Treatment may resume in this setting only upon resolution of immune AEs to baseline or improvement to Grade <2, and only if deemed clinically appropriate by the treating physician and agreed to by the sponsor. If steroids cannot be tapered as outlined in [Attachment 7](#), and/or AEs do not resolve to < Grade 2, the patient may not be resumed on study treatment.

For the purposes of documentation, the investigator must assess if the toxicity is considered at least possibly related to study treatment (that is, the combination regimen) and if the AE is considered to be immune related. Investigators are encouraged to consult the sponsor for additional guidance.

For AEs that are considered at least possibly related to study treatment, the following dose adjustment guidance may be applied:

- Treat each of the toxicities with maximum supportive care (including holding the study drug[s] suspected of causing the toxicity where required).
- If the symptoms promptly resolve with supportive care, consideration should be given to continuing the same dose of study drugs along with appropriate continuing supportive care.
- All dose modifications should be documented with clear reasoning and documentation of the approach taken.

In addition, there are certain circumstances in which study drugs should be permanently discontinued (refer to [Attachment 7](#)).

Following the first dose of study drugs, subsequent administration of study drugs can be modified based on toxicities observed (refer to [Attachment 7](#)).

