7.2.1. Dosing Schedule

Refer to Section [7.2.2](#) for Part A (dose escalation) dose regimens for each combination, by cohort. Refer to Section [7.2.3](#) for Part B (disease-specific expansion) dose regimens for LY3022855-plus-durvalumab, by cohort.

For each combination regimen, LY3022855 will be administered first, followed by a 30-minute observation period. After the observation period, durvalumab or tremelimumab will be administered. In this study, a cycle is defined as 4 weeks (28 days); Day 1 of a cycle is based on the administration of LY3022855 (rather than durvalumab or tremelimumab). A delay of study treatment due to holiday, weekend, bad weather, or other unforeseen circumstances will be permitted for a maximum of 3 days and not counted as a protocol deviation.

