7.2.1.1. LY3022855

Eligible patients will receive LY3022855 as an I.V. infusion administered over a minimum duration of 30 minutes and a maximum duration of 4 hours, based on the known safety and stability of the prepared drug. The infusion rate should not exceed 25 mg/minute. Suggested infusion times are as follows:

- 90 minutes for the first infusion; if no infusion-related reaction (IRR) is observed, decrease the infusion time to 60 minutes for the second infusion
- 60 minutes for the second infusion; if no IRR is observed, decrease the infusion time to 30 minutes for the third infusion
- 30 minutes for the third and subsequent infusions

If, at any time, a patient experiences an IRR, the infusion time should not be decreased.

Premedication is not recommended to be administered prior to the first infusion of LY3022855. However, if the patient experiences a Grade 1 or 2 IRR, premedication must be provided prior to any subsequent doses of LY3022855. The choice of premedication is to be made after discussion and agreement between the investigator and sponsor. In such cases (Grade 1 or 2 IRRs), administration of steroids should be avoided, if possible. If an IRR Grade ≤ 2 occurs during or after LY3022855 administration and the patient's condition allows it, treatment with durvalumab or tremelimumab will proceed as planned. Patients experiencing an IRR Grade ≥ 3 will be permanently discontinued from study treatment.

LY3022855 may be administered up to 3 days AFTER the scheduled dosing date and up to 4 days BEFORE the next scheduled dosing date to accommodate for patient vacations, holidays, inclement weather or other unforeseen circumstances. If, at any time, a dose is to be administered beyond the 3-day window, that dose is to be skipped. A maximum of 28 days between administered doses is allowed for delays due to adverse events.

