7.2.1.2. Durvalumab

Patients are to receive durvalumab I.V. on Days 1 and 15 of every cycle. Durvalumab may be administered up to 3 days AFTER the scheduled dosing date. If, at any time, a dose is administered beyond the 3-day window, that dose is considered a dose delay. A maximum delay of 28 days between administered doses is allowed (for dose delay in case of immune-related AE

please refer to Section 7.2.4.1). Note that a maximum of 12 months/26 doses of durvalumab treatment is permitted.

Refer to [Attachment 9](#) for the durvalumab dose volume calculation.

Durvalumab will be administered at room temperature (approximately 25°C) by controlled infusion via an infusion pump into a peripheral or central vein. Following preparation of durvalumab, the entire contents of the I.V. bag should be administered as an I.V. infusion over approximately 60 minutes (± 5 minutes), using a 0.2- or 0.22- μ m in-line filter. Less than 55 minutes is considered a deviation.

The I.V. line will be flushed with a volume of I.V. solution (0.9% [w/v] saline) equal to the priming volume of the infusion set used after the contents of the I.V. bag are fully administered, or complete the infusion according to institutional policy to ensure the full dose is administered and document if the line was not flushed.

A 1-hour observation period is required after the first infusion of durvalumab. If no clinically significant infusion reactions are observed during or after the first cycle, subsequent infusion observation periods can be at the investigator's discretion (suggested 30 minutes after each durvalumab infusion).

Patients will be monitored during and after the infusion with assessment of vital signs at the times specified in this study protocol.

In the event of a Grade ≤ 2 IRR, the infusion rate of study drug may be decreased by 50% or interrupted until resolution of the event and re-initiated at 50% of the initial rate until completion of the infusion. For patients with a Grade ≤ 2 IRR, subsequent infusions may be administered at 50% of the initial rate. Acetaminophen and/or an antihistamine (for example, diphenhydramine) or equivalent medications per institutional standard may be administered at the discretion of the investigator. If the IRR is Grade ≥ 3 in severity, study drug will be permanently discontinued.

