7.2.1.3. Tremelimumab

Patients are to receive tremelimumab I.V. on Day 1 of every cycle for the first 6 doses (Cycles 1-6). Starting with Cycle 7 (4 weeks after Dose 6 [Week 25]), tremelimumab will be dosed once every 3 cycles (12 weeks), that is, on Day 1 of Cycles 7, 10, 13, and so on, until disease progression.

Tremelimumab may be administered up to 3 days AFTER the scheduled dosing date. If, at any time, a dose is administered beyond the 3-day window, that dose is considered a dose delay. A delay of up to 28 days between administered doses is allowed for Cycles 1 through 6, and up to 60 days between doses for Cycles 7 and beyond.

Refer to [Attachment 9](#) for the tremelimumab dose volume calculation.

Tremelimumab will be administered at room temperature (approximately 25°C) by controlled infusion via an infusion pump into a peripheral or central vein. Following preparation of tremelimumab, the entire contents of the I.V. bag should be administered as an I.V. infusion over

approximately 60 minutes (± 5 minutes), using a 0.2- or 0.22- μm in-line filter. Less than 55 minutes is considered a deviation.

The I.V. line will be flushed with a volume of 0.9% (w/v) saline equal to the priming volume of the infusion set used after the contents of the I.V. bag are fully administered, or complete the infusion according to institutional policy to ensure the full dose is administered and document if the line was not flushed.

In the event that either preparation time or infusion time exceeds the time limits presented in this section, a new dose must be prepared from new vials. Tremelimumab does not contain preservatives, and any unused portion must be discarded.

A 1-hour observation period is required after the first infusion of tremelimumab. If no clinically significant infusion reactions are observed during or after the first cycle, subsequent infusion observation periods can be at the investigator's discretion (suggested 30 minutes after each tremelimumab infusion).

Patients will be monitored during and after the infusion with assessment of vital signs at the times specified in this study protocol.

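### For an adverse event outside the immune-related exception, one missed every-12-week tremelimumab dose may be given up to 60 days late under Sections 7.2.1.3 and 6.3.2 but ends the drug under Section 7.2.4.1

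*Protocol*

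**What the plan says.** The three drug-specific sections deal differently with a dose that misses its 3-day window.

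- LY3022855 (Protocol 7.2.1.1): "If, at any time, a dose is to be administered beyond the 3-day window, that dose is to be skipped".
- Durvalumab (7.2.1.2): a dose given after the window is kept, and "that dose is considered a dose delay". The limit is 28 days. Only delays for immune-related events are referred to Section 7.2.4.1.
- Tremelimumab (7.2.1.3): "If, at any time, a dose is administered beyond the 3-day window, that dose is considered a dose delay". The limit is 28 days in Cycles 1 to 6 and 60 days from Cycle 7. Section 6.3.2 repeats both limits among the discontinuation criteria. Neither section restricts them by reason.

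Section 7.2.4.1 covers delays for adverse events and applies to all study drugs. A hold may last at most 28 days, and the dosing calendar runs on regardless of the hold. After recovery, "the study drugs should be resumed per the original schedule". It then states: "If the original schedule results in a study drug being held for >28 days, the study drug may not be resumed". There is no 60-day allowance for tremelimumab. The one exception is an immune-related event managed and documented per Attachment 7, for which the hold may exceed 28 days while steroids are tapered.

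**The concern.** For the partner drugs, Sections 7.2.1.2 and 7.2.1.3 describe a late dose. Section 7.2.4.1, by fixing the calendar, turns the same dose into a skipped one. Where the next slot is more than 28 days away it also removes the drug. Two patients with the same event and the same recovery could therefore have different treatment histories, depending on which section is applied.

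Tolerability of each combination is a primary objective, and the choice feeds into its descriptive measures: treatment duration, discontinuations for adverse events, dose intensity and relative dose intensity. SAP Section 6.8.1 defines relative dose intensity as actual over planned amount but does not say whether a late, skipped or barred dose stays in the planned amount. For durvalumab the timing could also matter in Cycle 1, because Section 7.6.1 ties evaluability for dose-limiting toxicity to receipt of all Cycle 1 doses.

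**Working it through.** The check is calendar arithmetic.

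1. **Reproduce the stated date.** Section 7.2.1: "a cycle is defined as 4 weeks (28 days"). Study day of Cycle c Day 1 = (c − 1) × 28 + 1. For Cycle 7 this is 6 × 28 + 1 = Day 169. The week is (169 − 1)/7 + 1 = 25, which matches Section 7.2.1.3: "Starting with Cycle 7 (4 weeks after Dose 6 [Week 25"]).
2. **Slots from Cycle 7.** Section 7.2.1.3: "tremelimumab will be dosed once every 3 cycles (12 weeks"), that is Cycles 7, 10 and 13, or Days 169, 253 and 337. The spacing is 84 days.
3. **Section 7.2.4.1, one missed dose.** Hold = next original slot minus missed slot.
   - Cycle 7 missed: 253 − 169 = 84 days.
   - Cycle 10 missed: 337 − 253 = 84 days.
   - Both exceed 28. Counting from the last tremelimumab dose actually given makes the gap longer: 253 − 141 = 112 days and 337 − 169 = 168 days. On either count, resumption is barred outside the immune-related exception.
4. **Sections 7.2.1.3 and 6.3.2, same missed dose.** The text speaks of 60 days between doses. The planned interval is already 84 days, so this has to mean 60 days past the due date. A Cycle 7 dose due on Day 169 may then be given up to Day 169 + 60 = 229.
5. **Extent of the disagreement.** A dose 4 to 28 days late (25 day-values) is inside both limits but off the calendar that Section 7.2.4.1 keeps. A dose 29 to 60 days late (60 − 28 = 32 day-values) is inside one limit and outside the other.
6. **Tremelimumab in Cycles 1 to 6.** The next slot is 28 days after the missed one. That is not more than 28, so the drug may resume at that slot. The sections disagree only on whether the dose may be given before it.
7. **Durvalumab, Days 1 and 15.** One missed dose is a 14-day hold and two in a row are 28 days. Both sections use a 28-day limit, so one missed dose again gives a difference of timing only.

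**The case against.** The best defence is a division of scope. Section 7.2.4 sends the reader to 7.2.4.1 for delays due to adverse events, so 7.2.1.2 and 7.2.1.3 could be read as general administration windows. Section 7.2.4 also permits interruptions unrelated to treatment, so a 60-day allowance would still have a use. This reading is possible, but the text does not state it. Section 6.3.2 gives the 60-day limit as a discontinuation criterion for any delay. Section 7.2.1.2 refers only immune-related delays to 7.2.4.1, and 7.2.1.3 refers none. Section 7.2.1.1 shows that the protocol names adverse events as the reason when it means to.

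A reader might infer that every patient who misses an every-12-week dose for an adverse event loses tremelimumab. The documents do not support that. Section 7.2.4.1 exempts immune-related events managed per Attachment 7, and the tremelimumab events of special interest are largely of that kind.

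Attachment 7 narrows the field further. After a Grade 3 non-immune event, treatment resumes on improvement to Grade 2 or lower within 7 days or resolution within 14 days, and otherwise stops. In some asymptomatic AST or creatine kinase elevations the partner drug continues or may resume while LY3022855 is held. This makes long tremelimumab holds less common but does not remove the conflict. For an asymptomatic Grade 2 creatine kinase rise, Attachment 7 holds both drugs and resumes both if the work-up is clean. If that hold outlasts the window at Cycle 7 Day 1, Attachment 7 says resume, 7.2.1.3 allows a late dose, and 7.2.4.1 bars the drug. Section 5.1.2 reports creatine kinase rises in 17 of 64 LY3022855 monotherapy patients.

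Resumption after an adverse event also needs sponsor agreement, so the outcome is not left to each site alone. That should reduce inconsistency, but the sponsor would be applying the same conflicting text.

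**Conclusion.** The contradiction is in the current text. For an adverse event outside the immune-related exception, one missed tremelimumab dose from Cycle 7 may be given up to 60 days late under 7.2.1.3 and 6.3.2, or leads to an 84-day hold and permanent loss of the drug under 7.2.4.1. For durvalumab and four-weekly tremelimumab, a single missed dose raises a question of timing only.

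The reach of the permanent-stop effect is small. It concerns Part A tremelimumab patients (about 12 to 42 planned) who are still treated at Week 25, and the documents do not say how many that will be. It comes after the Cycle 1 toxicity window and cannot alter the maximum tolerated dose. The analyses it touches are descriptive.

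Two assumptions matter. The 60 days are read as lateness past the due date. The 28-day hold for four-weekly tremelimumab is counted from the due date of the missed dose. Section 7.2.4.1 also asks for recovery within 28 days of the last administered dose without saying which drug's dose. A reader might want a single figure in days for the four-weekly timing difference, but the text does not fix one.

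**What to change.** Reconcile Sections 6.3.2, 7.2.1.2, 7.2.1.3 and 7.2.4.1 with the resume and discontinue rules for non-immune events in Attachment 7. The result should be one rule per drug stating:

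- whether a dose missed for an adverse event is given late or skipped;
- which delay limit applies to tremelimumab on the 12-week schedule, and from which date it is counted.

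Then add a line to SAP Section 6.8.1 deriving the planned amount for relative dose intensity from that rule. Which rule is right is for the sponsor to decide. The cost is protocol wording and one SAP derivation line. Amendment (c) already set out to make the delay criteria consistent across the protocol, so this would complete that work.

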7.2.4.1.1. Specific Adverse Events

Adverse events of special interest (AESIs) observed with durvalumab and/or tremelimumab include colitis; pneumonitis; alanine aminotransferase (ALT)/AST increases; hepatitis/hepatotoxicity; neuropathy/neuromuscular toxicity (that is, events of encephalitis, peripheral motor and sensory neuropathies, Guillain-Barré, and myasthenia gravis); endocrinopathy (that is, events of hypophysitis, adrenal insufficiency, hyperthyroidism, and hypothyroidism; type 1 diabetes mellitus); dermatitis; nephritis; and pancreatitis (or labs suggestive of pancreatitis-increased serum lipase or serum amylase); other inflammatory responses that are rare with a potential immune-mediated etiology include, but are not limited to, myocarditis, pericarditis, myositis/polymyositis, and uveitis. Refer to [Attachment 8](#) for details about and management of AESIs.

Guidelines for the management of immune-mediated, infusion-related, and non-immune-related AEs are shown in [Attachment 7](#).

Adverse events (both nonserious and serious) associated with study drugs may represent an immune-related etiology, which may be based on the mechanism of action of study drugs leading to T cell activation and proliferation. These irAEs may occur shortly after the first dose or several months after the last dose of treatment. Potential irAEs include immune-mediated enterocolitis, dermatitis, hepatitis, and endocrinopathies. Patients should be monitored for signs and symptoms of irAEs. In the absence of an alternative etiology (for example, infection or progressive disease), signs or symptoms of enterocolitis, dermatitis, pneumonitis, hepatitis, myocarditis, myopathy/polymyopathy and endocrinopathy should be considered immune related. Refer to [Attachment 7](#) for supportive care guidelines for immune-mediated reactions, including use of corticosteroids.

Based on observations from clinical trials with LY3022855, patients receiving study treatment should be closely monitored for signs of hepatic function impairment (for example, increases in transaminases, lactate dehydrogenase [LDH], bilirubin, coagulation disorders) and creatine kinase increases.

As with any antibody, allergic reactions to dose administration are possible. Appropriate drugs and medical equipment to treat acute anaphylactic reactions must be immediately available, and study personnel must be trained to recognize and treat anaphylaxis. The study site must have immediate access to emergency resuscitation teams and equipment in addition to the ability to admit patients to an intensive care unit if necessary. Refer to [Attachment 7](#) for management of infusion-related AEs.

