5.4. Rationale for Selection of Dose

5.4.1. LY3022855

Clinical experience with LY3022855 comprises 43 patients (as of 28 Jan 2016) who received the following doses intravenously (I.V.): 2.5 mg/kg weekly (QW) (n=6), 0.3 mg/kg QW (n=4), 0.6 mg/kg QW (n=3), 1.25 mg/kg every 2 weeks (Q2W) (n=20), 1.25 mg/kg QW (n=5), and 1 mg/kg on Weeks 1, 2, 4, and 5 of every 6-week cycle (n=5) in 2 ongoing Lilly-sponsored Phase 1 studies (I5F-IE-JSCA [JSCA] and I5F-MC-JSCB [JSCB]). At the first human dose studied, 2.5 mg/kg QW, which was also the highest dose administered, laboratory abnormalities were noted in 5 patients (Grade 2-3 creatine kinase or Grade 2-3 aspartate aminotransferase [AST] elevations) but were not classified as dose-limiting toxicities (DLTs) due to the lack of clinical signs or symptoms of organ toxicity. Because of these laboratory abnormalities, the study protocol was amended and dose escalation was restarted at a lower dose, 0.3 mg/kg QW. Three dose-limiting toxicities (DLTs) have been observed in Study JSCA: an event of left ventricular dysfunction in Cohort 4 (1.25 mg/kg Q2W) and separate events of pancreatitis and rhabdomyolysis in Cohort 5 (1.25 mg/kg QW). Upon further review, the patient with the DLT of left ventricular dysfunction had a baseline LVEF of 35%, which obfuscated the relationship between LY3022855 and the DLT event; therefore, the patient was considered to be a suboptimal candidate for study participation. No DLTs have occurred at the other dose levels.

In addition, elevated CK, AST, and LDH levels were observed in patients treated with LY3022855 at 2.5 mg/kg QW (JSCA), as previously stated, and at 1.25 mg/kg Q2W (JSCB). However, enzyme levels decreased to Grade <2 upon discontinuation of LY3022855, indicating that these effects were reversible.

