Attachment 1. Protocol JSCC Study Schedule

Assessments are to be performed at the times stipulated in the schedule and as clinically required in the management of the patient.

Screening/Baseline Assessments (Visit 0)

Relative Day Prior to Day 1 of Cycle 1	≤28	≤14	≤7	Comments
Written informed consent/assignment of patient identification number	X			ICF signed (prior to performance of any protocol-specific tests/procedures).
Review of eligibility criteria	X			
Medical history		X		
Physical examination		X		Full physical examination, including assessments of the head, eyes, ears, nose, and throat and the respiratory, cardiovascular, GI, urogenital, musculoskeletal, neurological, dermatological, hematologic/lymphatic, and endocrine systems.
Vital signs		X		BP, temperature, RR, and PR. Includes height (at baseline only) and weight.
ECOG performance status		X		
ECG (local)		X		Triuplicate ECG will be obtained, on which QTcF must be <470 ms (calculated from one ECG using Fridericia's Correction Formula and confirmed with 2 additional ECGs).
HIV screening (local)	X			Per institutional standards. If done within 28 days prior to Cycle 1, Day 1, as part of standard of care, does not need to be repeated prior to the start of Cycle 1.
Hematology (local)		X		Refer to Attachment 2 .
Serum chemistry (central)		X		Refer to Attachment 2 .
Urinalysis (local)		X		Refer to Attachment 2 .
Coagulation (local)		X		Refer to Attachment 2 . Obtain prior to tumor biopsy.
Thyroid function (central)		X		Refer to Attachment 2 . Free T3 and free T4 will be measured only if TSH is abnormal or if there is clinical suspicion of an AE related to the endocrine system.
Pancreas function (central)		X		Refer to Attachment 2 .
LVEF evaluation	X			Echocardiogram or MUGA scan.
Radiographic tumor assessment (CT/MRI)	X			If done within 28 d prior to Cycle 1, Day 1, as part of standard of care, does not need to be repeated prior to the start of Cycle 1.
Tumor measurement (palpable or visible)		X		
CTCAE v4.0 grading (preexisting conditions)		X		To be reported only after study eligibility is confirmed. Refer to Section 8.1.2.4 for reporting guidelines.
Concomitant medications		X		

Relative Day Prior to Day 1 of Cycle 1	≤28	≤14	≤7	Comments
Tumor markers (local)		X		As clinically indicated. For example, CEA in patients with colorectal cancer or CA125 in patients with ovarian cancer.

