Whole blood	X		X		X		Gene expression analysis and other exploratory research.
Flow cytometry							
Immunophenotyping #1	X			X	X	X	CD14 and CD16.
Immunophenotyping #2	X			X	X	X	TBNK & T cell subset/activation panels.
Immunophenotyping #3	X						MDSC panel.
Isoenzymes (central)							Refer to Attachment 2 . Obtain at additional time points, as clinically indicated.

LY3022855 plus Durvalumab Assessment (central or local laboratory indicated, if applicable)	Cycle 1 (Visit 1)						Comments Except for the Cycle 1, Day 1 visit, allowable windows are ± 3 days, unless otherwise indicated. On dosing days, all assessments to be performed preinfusion, unless stated otherwise.
	1	2	3	8	15	22	
Relative day within a 28-day cycle:	1	2	3	8	15	22	
LVEF evaluation							Echocardiogram or MUGA scan. Obtain at additional time points, as clinically indicated.
Radiographic tumor assessment (CT/MRI)							Perform every 8 wk (± 7 d), starting on Cycle 2, Day 22.
Tumor measurement (palpable or visible)							
Tumor biopsy							For Part A (all cohorts) and Part B (ovarian cancer cohort only): An on-treatment tumor core needle or excisional biopsy to be performed 6-8 wk after starting study treatment.

LY3022855 plus Durvalumab Assessment (central or local laboratory indicated, if applicable)	Cycle 2 (Visit 2)						Comments Except for the Cycle 1, Day 1 visit, allowable windows are ± 3 days, unless otherwise indicated. On dosing days, all assessments to be performed preinfusion, unless stated otherwise.
	1	8	9	10	15	22	
Relative day within a 28-day cycle:							
Physical examination	X	X			X	X	Targeted physical examination (on the basis of clinical observations and symptomatology).

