LY3022855 plus Durvalumab Assessment (central or local laboratory indicated, if applicable)	Cycle 2 (Visit 2)						Comments Except for the Cycle 1, Day 1 visit, allowable windows are ± 3 days, unless otherwise indicated. On dosing days, all assessments to be performed preinfusion, unless stated otherwise.
	1	8	9	10	15	22	
Relative day within a 28-day cycle:							
Isoenzymes (central)	X						Refer to Attachment 2 . Obtain at additional time points, as clinically indicated.
LVEF evaluation						X	Echocardiogram or MUGA scan. Obtain at additional time points, as clinically indicated.
Radiographic tumor assessment (CT/MRI)						X	Perform every 8 wk (± 7 d), starting on Cycle 2, Day 22.
Tumor measurement (palpable or visible)						X	
Tumor biopsy		X					For Part A (all cohorts) and Part B (ovarian cancer cohort only): An on-treatment tumor core needle or excisional biopsy to be performed 6-8 wk after starting study treatment; that is, at Cycle 2, between Days 8 and 22. For Part B (NSCLC cohort) an optional on-treatment tumor tissue should be collected from patients in the study where possible.

LY3022855 plus Durvalumab Assessment (central or local laboratory indicated, if applicable)	Cycle 3 (Visit 3)				Cycle 4 (Visit 4)				Cycle 5 (Visit 5)				Comments Except for the Cycle 1, Day 1 visit, allowable windows are ± 3 days, unless otherwise indicated. On dosing days, all assessments to be performed preinfusion, unless stated otherwise.
	1	8	15	22	1	8	15	22	1	8	15	22	
Relative day within a 28-day cycle:	1	8	15	22	1	8	15	22	1	8	15	22	
Physical examination	X				X				X				Targeted physical examination (on the basis of clinical observations and symptomatology).

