Attachment 2. Protocol JSCC Clinical Laboratory Tests

Clinical Laboratory Tests - Assayed by Local Laboratory (local or investigator-designated laboratory)

Hematology

Hemoglobin
Hematocrit
Erythrocyte count (RBC)
Leukocytes (WBC)
Neutrophils
Lymphocytes
Monocytes
Eosinophils
Basophils
Platelets
Mean corpuscular hemoglobin
Mean corpuscular hemoglobin concentration
Mean corpuscular volume

Serum Chemistry

Sodium
Potassium
Chloride
Bicarbonate
Total bilirubin
Alkaline phosphatase
Alanine aminotransferase (ALT)
Aspartate aminotransferase (AST)
Albumin
Total protein
Blood urea nitrogen
Creatinine
Glucose, random
Creatine kinase

Coagulation

aPTT
PT, INR

Urinalysis^a

Specific gravity
pH
Protein
Glucose
Ketones
Blood
Urine leukocyte esterase
Nitrites
Bilirubin
Color and appearance

Serum or Urine Pregnancy Test (females only)

Myoglobin

Serum myoglobin
Urine myoglobin

Serologies

HIV screening

**Clinical Laboratory Tests - Assayed by Central Laboratory^b
(sponsor-designated laboratory)**

Serum Chemistry

Sodium
Magnesium
Potassium
Calcium
Chloride
Bicarbonate
Total bilirubin^c
Alkaline phosphatase
Alanine aminotransferase (ALT)
Aspartate aminotransferase (AST)
Gamma-glutamyl transpeptidase (GGT)^d
Albumin
Total protein
Blood urea nitrogen
Creatinine
Uric acid
Glucose, random
Creatine kinase

Thyroid Function

Thyroid-stimulating hormone
Free T3
Free T4
Isoenzymes
Alkaline phosphatase isoenzymes
Total creatine kinase
Creatine kinase isoenzymes
Total LDH
LDH isoenzymes

Pancreas Function

Amylase
Lipase

Abbreviations: aPTT = activated partial thromboplastin time; HIV = human immunodeficiency virus; INR = international normalized ratio; LDH = lactate dehydrogenase; PT = prothrombin time; T3 = triiodothyronine; T4 = thyroxine; ULN = upper limit of normal.

^a Microscopy should be used as appropriate to investigate WBCs and use the high power field for RBCs.

^b Results will be confirmed by the central laboratory at the time of initial testing.

^c If total bilirubin $\geq 2 \times$ ULN (and no evidence of Gilbert's syndrome), fractionate into direct and indirect bilirubin.

^d At baseline and as clinically indicated.

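### LDH and the isoenzyme panel have one scheduled draw (Cycle 2 Day 1) and no scheduled baseline, so treatment-emergent change cannot be assessed systematically from scheduled samples

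*Protocol*

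**What the plan says.** Protocol 7.2.4.1.1, citing experience in earlier LY3022855 trials, says patients should be "closely monitored for signs of hepatic function impairment (for example, increases in transaminases, lactate dehydrogenase [LDH], bilirubin, coagulation disorders) and creatine kinase increases". The instruction is a recommendation, and LDH is one of several illustrative signs.

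The protocol treats LDH as a known finding. Section 5.4.1 states that "elevated CK, AST, and LDH levels were observed in patients treated with LY3022855", at two monotherapy regimens. Section 5.1.2 describes a monotherapy patient discontinued for drug-related rises in CK, AST and LDH. It also names LDH with CK and AST as enzymes raised by CSF-1R antibodies as a class.

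Attachment 2 lists the tests. Transaminases, bilirubin and CK are in both the local and the central serum chemistry panels. LDH is in neither. Total LDH and "LDH isoenzymes" appear only in the central Isoenzymes panel, with total CK, CK isoenzymes and alkaline phosphatase isoenzymes.

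Attachment 1 has no isoenzyme or LDH row at screening. In each combination's schedule the Isoenzymes row carries a single mark, at Cycle 2 Day 1. It is unmarked in Cycle 1, from Cycle 3 onward and at follow-up. The row's comment adds: "Obtain at additional time points, as clinically indicated".

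SAP 6.1 defines baseline as the last value reported before the first dose. SAP 6.2 imputes no missing data other than dates.

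**The concern.** Of the signs named in 7.2.4.1.1, transaminases, bilirubin and CK have a screening value and frequent repeats, and coagulation is scheduled at screening and at Cycle 2 Day 1. LDH alone has no scheduled baseline. A single value about four weeks after the first dose cannot show whether LDH rose on treatment. No eligibility criterion bounds LDH at entry, whereas exclusion criterion 27 keeps out patients with CK above normal. A raised LDH at Cycle 2 Day 1 therefore cannot be told apart from one already present.

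The first primary objective is to characterise the safety of each combination. Three enzymes, CK, AST and LDH, are described together as the drug's laboratory signal. The plan follows two of them closely and samples the third once.

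**Working it through.** No formula is involved. The check is a count of scheduled draws in Attachment 1, using the panel contents in Attachment 2.

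| Scheduled time | Isoenzymes panel incl. LDH (either combination) | Central chemistry, durvalumab | Central chemistry, tremelimumab |
|---|---|---|---|
| Screening | 0 | 1 | 1 |
| Cycle 1 Day 1, pre-infusion | 0 | 1 | 1 |
| Rest of Cycle 1 (Days 2, 8, 15, 22) | 0 | 4 | 4 |
| Cycle 2 (Days 1, 8, 15, 22) | 1 (Day 1) | 4 | 4 |
| Cycle 3 | 0 | 4 | 4 |
| Cycle 4 | 0 | 4 | 4 |
| Cycle 5 | 0 | 1 | 2 |
| Total | 1 | 19 | 20 |

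1. **Baseline.** Central chemistry has 1 + 1 = 2 scheduled pre-dose draws, or 1 if screening safety tests fall within 72 hours of Cycle 1 Day 1 and are not repeated. The Isoenzymes panel has 0.

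2. **DLT window.** The window is 28 days from Cycle 1 Day 1. Central chemistry has 4 scheduled post-dose draws in it (Days 2, 8, 15, 22); the Isoenzymes panel has 0. Cycle 2 Day 1 is Study Day 28 + 1 = 29. The ±3-day visit window lets the actual draw fall between Days 26 and 32, so an early visit could just reach the end of the window, but none is planned inside it.

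3. **Cycles 1 and 2 together.** After the first dose there are 4 + 4 = 8 scheduled central values for CK, AST, ALT and bilirubin, against 1 for LDH. A patient who stops before Cycle 2 Day 1 has no scheduled LDH at all, because the follow-up visits are also unmarked.

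4. **Change from baseline.** With no scheduled pre-dose value and no imputation, scheduled samples give an LDH or isoenzyme change in 0 of the up to approximately 118 patients planned in Protocol 10.1.

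5. **Do triggered work-ups fill the gap?** Mostly they do not call for LDH. The Attachment 3 hepatic tests omit it. In Attachment 7, the hepatitis guidance lists AST, ALT, ALP and bilirubin, and the CK evaluation lists myoglobin, BUN and creatinine. Attachment 7 names LDH only when poly/myositis is suspected. Each of these comes after an event.

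**The case against.** The strongest reply is that this is an ancillary measure and nothing in the plan turns on it. Much of that is right.

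- **Wording.** Section 7.2.4.1.1 recommends monitoring and gives LDH as an example. A reader might infer a binding LDH requirement that the schedule breaks; the text does not support that. Most of the other listed signs are well covered.
- **On-demand draws.** The schedule provides for extra isoenzyme samples when clinically indicated, so more LDH values may exist. They would be event-driven, however, and cannot recover a pre-dose value.
- **Source of CK and AST rises.** A reader might infer that tissue source cannot be determined. That does not follow. CK must be within normal limits at entry, and myoglobin is tested at CK Grade 2 or higher. Attachment 7 requires a diagnostic evaluation for asymptomatic Grade 2 and 3 CK. Isolated AST rises are judged against ALT and bilirubin, and CK isoenzymes can be drawn at the time of a rise. The panel holds no AST isoenzyme, so drawing it more often would inform AST source only indirectly.
- **Amendment (b).** A reader might see the isoenzymes as the test of the Kupffer-cell explanation behind the relaxed DLT criteria. The protocol never gives them that role.
- **Decisions.** LDH appears in no DLT criterion in 7.2.2.1 and in no AST or CK dose-modification rule in Attachment 7.
- **SAP.** Section 6.8.5 plans listings and graded abnormalities by visit and cohort, not laboratory change from baseline. No specified LDH analysis becomes impossible.

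These points limit what is at stake. They do not supply a baseline or a scheduled value in the DLT window.

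**Conclusion.** The concern holds within limits. As scheduled, each patient contributes 0 pre-dose LDH values, 0 at visits planned in the DLT window and 1 at nominal Day 29, and the isoenzymes follow the same pattern. Treatment-emergent change in either cannot be assessed systematically from scheduled samples in either combination. The schedule is out of line with 7.2.4.1.1 and with the protocol's own account of LDH as a signal of this drug.

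It would be wrong to infer that DLT assessment, the MTD or the RP2D is compromised: no rule behind them uses LDH. The loss is in describing a known laboratory effect. The change is worth making because it is small, and a missing pre-dose value cannot be obtained later.

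The counts assume that column positions in the machine-read tables are right. Both combinations agree, and the absence of a screening row does not depend on column position. The counts cover scheduled samples only; how many unscheduled LDH values would be taken is unknown.

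**What to change.** Reconcile Protocol 7.2.4.1.1 with Attachments 1 and 2:

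1. Add total LDH to the central serum chemistry panel in Attachment 2. It is then measured at screening and wherever central chemistry is already scheduled. That is not every visit day: in the durvalumab schedule, Cycle 5 has Day 1 only and later cycles have Days 1 and 15. Scheduled LDH draws through Cycle 5 rise from 1 to 19 (durvalumab) or 20 (tremelimumab).
2. Mark the Isoenzymes panel pre-dose at Cycle 1 Day 1 in both schedules and keep Cycle 2 Day 1. Scheduled isoenzyme draws go from 1 to 2, giving a paired baseline.
3. Include LDH, with its baseline value and change from baseline, in the SAP 6.8.5 laboratory summaries.

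The cost is one more analyte on existing draws, one more isoenzyme panel per patient at an existing visit, and edits to the schedule, laboratory list and SAP. No visit is added, and no dosing or management rule changes.
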